4. SYNOPSIS

Title of Study:	PMCF Study on PEEK Suture Anchors for Hip Indications					
Study Design:	Multi-center, retrospective case series.					
Study Type:	Post-market Clinical Follow-up					
Study Products:	
PEEK Suture Anchors for Hip *Part numbers as of September 2018
 
 
 Bioraptor Knotless Suture Anchor	72202397	
 
 SpeedLock Hip Suture Anchor	OM-7500	
 
		Bioraptor Knotless Suture Anchor	72202397	SpeedLock Hip Suture Anchor	OM-7500
Bioraptor Knotless Suture Anchor	72202397					
SpeedLock Hip Suture Anchor	OM-7500					
Intended Use:	The PEEK anchors are intended to be used for soft tissue to bone fixation in the hip following hip capsule repair.					
Study Purpose:	Assess safety and performance post-market of the PEEK suture anchor devices to address clinical data gaps for MDR.					
Primary Outcome:	Evidence of safety and performance of the PEEK suture anchor devices in the hip.					
Statistical Rationale:	The sample size for this study is determined based on the feasibility of recruitment, enrolment and follow-up considerations. The study is therefore not powered for any statistical hypothesis testing but will be able to estimate a clinical success rate of 91% with a 95% confidence interval (CI) of 80% to 100%.					
Sample Size:	
Minimum number of subjects, n=40
 
Maximum number of subjects, n=240
 
Enrollment distribution:
 
Up to three sites will enroll a maximum of 40 subjects per anchor configuration therefore no more than 120 subjects will be enrolled for any anchor type.
					

CONFIDENTIAL AND PROPRIETARY

This document contains information that is confidential and proprietary to Smith & Nephew PLC and Smith & Nephew, Inc. and is intended for use only by Smith & Nephew and its manufacturer. It shall not be reproduced or copied in whole or in part, nor shall the contents be disclosed by any means without prior written permission from Smith & Nephew, nor shall anyone make any use of it that is contrary to the expressed or implied wishes of Smith & Nephew.

Study Protocol—Device	
PMCF Study on PEEK Suture Anchors for Hip Indications	Number: 2018.14.SMD.PEEK.RET.HIP
	Version: 2.0, 03 April 2019
	Page: 21 of 63

	PEEK Anchor	Minimum Number of Subjects/Site	Maximum Number of Subjects/Site	Maximum Number of Subjects for the Study
	Bioraptor Knotless Suture Anchor	20 subjects per site	40 subjects per site	120 subjects
	SpeedLock Hip	20 subjects per site	40 subjects per site	120 subjects
	Total	40 subjects	80 subjects	240 subjects
Number of Study Sites:	Up to 6 sites			
Targeted Global Regions:	USA			
Inclusion Criteria:	
 1. Subjects who have undergone hip joint repair using the study devices. 2. Subjects aged 18 years and older at the time of surgery. 3. Subjects must have had a visit to their provider between 6 and 15 months post-operative. 			
Exclusion Criteria:	
 1. Subjects who are < 12 months post-operative. 2. Subject is entered in another investigational drug, biologic, or device study or has been treated with an investigational product within 30 days prior to surgery. 3. Subject had off-label use of the PEEK suture anchor during surgery. 			
Study Duration:	Twelve month follow-up			
Primary Endpoint:	Clinical success rate (%) at 6 months post-operative based on standard of care			
Secondary Endpoint:	Clinical success rate (%) at 12 months post-operative based on standard of care			
Exploratory Outcomes:	Surgeon Reported Outcomes based on data collected on the subject's medical chart as standard of care at study sites. These may include but not restricted to the following:			

CONFIDENTIAL AND PROPRIETARY

This document contains information that is confidential and proprietary to Smith & Nephew PLC and Smith & Nephew, Inc. and is intended for use only by Smith & Nephew and its manufacturer. It shall not be reproduced or copied in whole or in part, nor shall the contents be disclosed by any means without prior written permission from Smith & Nephew, nor shall anyone make any use of it that is contrary to the expressed or implied wishes of Smith & Nephew.

Study Protocol—Device	
PMCF Study on PEEK Suture Anchors for Hip Indications	Number: 2018.14.SMD.PEEK.RET.HIP
	Version: 2.0, 03 April 2019
	Page: 22 of 63

	
 • Range of Motion (ROM) 
 • Flexion • Extension • Abduction • Adduction • External/Internal Rotation • Pain assessed by VAS
Safety Endpoints:	
 • All AEs, SAEs and complications including intra-operative adverse events and complications. • Device related intervention • Device deficiency

CONFIDENTIAL AND PROPRIETARY

5. SCHEDULE OF EVENTS

Table 1: Schedule of Events

Schedule of Events	Chart Review	
	182 days post-op 6M (\pm 91 Days)	365 days post-op 12M (\pm 91 Days)
Informed Consent	X NA if waiver of consent granted by IRB	
Inclusion/Exclusion	X	
Demographics/Medical History	X	
VAS, ROM	X	X
Operative Data Collection	X	
Implant Status and / or Disposition	X	X
Concomitant Medications or Therapies ¹	X	X
AE, SAE and DevD Assessment	X	X
End of Study		X ²

¹ Any concomitant medications associated with an AE, SA(D)E will be recorded.

² End of Study CRF can be completed at 6 months if the subject did not have a 12-month visit.

CONFIDENTIAL AND PROPRIETARY

This document contains information that is confidential and proprietary to Smith & Nephew PLC and Smith & Nephew, Inc. and is intended for use only by Smith & Nephew and its manufacturer. It shall not be reproduced or copied in whole or in part, nor shall the contents be disclosed by any means without prior written permission from Smith & Nephew, nor shall anyone make any use of it that is contrary to the expressed or implied wishes of Smith & Nephew.

Study Protocol—Device	
PMCF Study on PEEK Suture Anchors for Hip Indications	Number: 2018.14.SMD.PEEK.RET.HIP
	Version: 2.0, 03 April 2019
	Page: 24 of 63

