12.3 STUDY ENDPOINTS

12.3.1 Primary Endpoint

The primary endpoint will be clinical success rate (%) at 6 months post-operative based on standard of care. Clinical success is defined as hip repairs without signs of device failure and/or re-intervention as assessed by the surgeon.

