13. STUDY PROCEDURES

13.1 6 MONTHS POST-OP CHART REVIEW

NOTE: Any subject, who meets the inclusion/exclusion criteria, will be assigned a subject number.

1. Subject should undergo the informed consent process and sign the informed consent *only* if a waiver of consent has not been approved by the IRB.
2. Screen the subject's chart for protocol inclusion/exclusion criteria.
3. Obtain demographic information and a medical history.
4. VAS, ROM.
5. Operative Data Collection – review operative case notes.
6. Implant Status / Disposition.
7. Document concomitant medications and/or therapies associated with an AE, SA(D)E
8. Review the subject's chart for AEs, SAEs and Device Deficiencies, including inter-operative. AEs, SAEs and DevDs should be documented from the time of surgery through the study duration.

CONFIDENTIAL AND PROPRIETARY

This document contains information that is confidential and proprietary to Smith & Nephew PLC and Smith & Nephew, Inc. and is intended for use only by Smith & Nephew and its manufacturer. It shall not be reproduced or copied in whole or in part, nor shall the contents be disclosed by any means without prior written permission from Smith & Nephew, nor shall anyone make any use of it that is contrary to the expressed or implied wishes of Smith & Nephew.

Study Protocol—Device	
PMCF Study on PEEK Suture Anchors for Hip Indications	Number: 2018.14.SMD.PEEK.RET.HIP
	Version: 2.0, 03 April 2019
	Page: 39 of 63

13.2 12 MONTHS POST-OP CHART REVIEW

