14.3 EFFICACY ANALYSIS

14.3.1 Analysis of Primary Endpoint

The rate (%) of clinical success of all the PEEK suture anchor devices combined at 6 months post-operative will be summarized as a frequency and percentage. A 95% two-sided exact CI for a single proportion will be presented using Clopper-Pearson's method [1]. The same type analysis would be carried out for each of the 2 different PEEK suture anchors used in the study. These

CONFIDENTIAL AND PROPRIETARY

This document contains information that is confidential and proprietary to Smith & Nephew PLC and Smith & Nephew, Inc. and is intended for use only by Smith & Nephew and its manufacturer. It shall not be reproduced or copied in whole or in part, nor shall the contents be disclosed by any means without prior written permission from Smith & Nephew, nor shall anyone make any use of it that is contrary to the expressed or implied wishes of Smith & Nephew.

Study Protocol—Device	
PMCF Study on PEEK Suture Anchors for Hip Indications	Number: 2018.14.SMD.PEEK.RET.HIP
	Version: 2.0, 03 April 2019
	Page: 41 of 63

analyses will be carried out using the per protocol population as the primary analysis population with the safety population used for sensitivity analysis.

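### The 6-month primary success rate is read at a visit anywhere from day 91 to day 273, with no event-date cut-off

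*Combined protocol and SAP*

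**What the plan says.** Section 12.3.1 states: "The primary endpoint will be clinical success rate (%) at 6 months post-operative based on standard of care". It adds: "Clinical success is defined as hip repairs without signs of device failure and/or re-intervention as assessed by the surgeon". Section 14.3.1 states: "The rate (%) of clinical success of all the PEEK suture anchor devices combined at 6 months post-operative will be summarized as a frequency and percentage", with a two-sided 95% Clopper-Pearson interval, and repeats the analysis for each anchor.

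Table 1 sets the two reviews at "182 days post-op 6M (\pm 91 Days") and "365 days post-op 12M (\pm 91 Days"), and collects implant status at both. In Section 13.1, "Implant Status / Disposition" is an item of its own. A later item in the same list covers safety recording: "AEs, SAEs and DevDs should be documented from the time of surgery through the study duration". The synopsis gives the study duration as "Twelve month follow-up".

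Section 11.3 excludes anyone less than 12 months from surgery. The window can therefore only date the visit being abstracted, not the day on which the chart is opened. The visit needed to qualify is at 3 to 15 months in Section 11.2 but at 6 to 15 months in the synopsis.

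No section says which visit supplies the 6-month status when several fall in the window, or which endpoint a dated failure belongs to.

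**The concern.** A success rate at 6 months should mean the proportion of hips free of failure and re-intervention by a fixed day. As written, it is status at whatever standard-of-care visit falls in a six-month-wide window. Two hips with the same history can be scored differently because their surgeons see patients at different times.

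- Re-intervention on day 240, window visit on day 265: the hip can be scored a 6-month failure although it was intact at day 182.
- Re-intervention on day 150, only window visit on day 95: the hip can be scored a 6-month success although it had failed by day 182.

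Each anchor comes from at most three sites (Section 12.1), so one site's follow-up habit can move that anchor's rate. Because every subject is at least 12 months from surgery, later events may already be in the chart when the 6-month form is completed. Only a date rule separates them from earlier ones.

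**Working it through.** **Inputs.** Windows of 182 ± 91 and 365 ± 91 days (Table 1); 91% assumed success, lower limit of 80%, and 20 to 120 subjects per anchor (Section 15); two-sided exact 95% interval (Section 14.3.1). The documents give no failure times, so everything in steps 3 to 5 is illustration under a stated assumption.

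**1. Windows.** 182 − 91 = 91 and 182 + 91 = 273; 365 − 91 = 274 and 365 + 91 = 456. The windows adjoin without overlap. Follow-up within the 6-month label varies by 273/91 = 3.

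**2. The plan's own figure.** Section 15 gives a 15.2% to 95% probability for 20 to 120 subjects. I read this as the chance that the lower limit is at least 80% when true success is 91%.
- n = 20 needs 20/20: 0.91^20 = 15.16%, which matches.
- n = 120 with the planned two-sided interval needs 105/120 (lower limit 80.2%; 104/120 gives 79.3%): P(X ≥ 105) = 92.7%.
- n = 120 with a one-sided 95% limit needs 104/120: 95.9%, closer to the stated 95%.

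That mismatch is a separate matter. The baseline here is the planned two-sided interval.

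**3. Assumption A: constant hazard, 91% success at day 182.** S(d) = 0.91^(d/182).

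| All hips read at | Success | P(lower limit ≥ 80%), n = 20 | n = 120 |
|---|---|---|---|
| day 91 | 0.91^0.5 = 95.4% | 38.9% | 99.99% |
| day 182 | 91.0% | 15.2% | 92.7% |
| day 273 | 0.91^1.5 = 86.8% | 5.9% | 47.8% |

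Relative to day 182, reading early adds 95.4 − 91.0 = 4.4 points and reading late removes 91.0 − 86.8 = 4.2. The two ends of the window differ by 8.6 points for the same device.

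With visits evenly spread over days 91 to 273, the mean is (S(91) − S(273)) / (−ln 0.91) = (0.9539 − 0.8681) / 0.0943 = 91.0%. The early and late errors then cancel.

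**4. Changing the hazard shape.** A Weibull curve through 91% at day 182 has S(273) = 0.91^(1.5^k). Shape k = 0.5 (failures concentrated early) gives 89.1%; k = 1.5 gives 84.1%.

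**5. Assumption B: failures on days 183 to 273 as a share of those by day 182, all hips read at day 273.** Success = 1 − 0.09 × (1 + share). Shares of 0%, 10%, 25% and 50% give 91.0%, 90.1%, 88.8% and 86.5%.

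**The case against.** A wide window is natural when charts follow standard of care, and Section 14 defers detail to an SAP to be finalized before database lock. The plan also separates its time points: the two windows do not overlap, and Section 14.5 summarizes on-study device-related failure and re-intervention apart from the 6-month rate. The interval is descriptive, the study is not powered for any test, and no comparison between anchors is specified. Section 15 does not tie the 91% to day 182, and the fall from 92.7% to 47.8% needs both a constant hazard and every hip read on the last day of the window. All of this stands, and it limits the size of the point. It does not supply the missing rule: the planned SAP is where the rule can go, not evidence that it exists.

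A reader might infer from the safety-recording instruction in Section 13.1 that every failure up to twelve months counts against the 6-month rate. The documents do not support that. The instruction governs adverse events and device deficiencies, is repeated word for word for the 12-month review in Section 13.2, and is not referred to in the success definition or the primary analysis. An event on day 300, for example, lies in the 12-month window.

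It is also fair to object that a chart reviewer could see a day-150 re-intervention even if the window visit was on day 95. Whether it is counted depends on how status at the visit is read, and the plan does not say.

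**Conclusion.** The point holds as a missing definition. The 6-month rate has no event-date cut-off and is read at a visit between day 91 and day 273, so follow-up varies threefold. Under the constant-hazard illustration the rate could lie anywhere from 95.4% to 86.8% according to visit timing alone, but it stays at about 91.0% if visits are evenly spread. If failures concentrate early, the late-side loss shrinks to about 1.9 points (91.0 − 89.1).

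A reader might infer that the rate is biased downward. That does not follow: early visits raise it, late visits lower it, and the net sign is unknown without the distribution of visits and failure times. Nor are the 6- and 12-month rates shown to merge. What is established is that the estimate can depend on site visit habits as well as on the anchor, and that the charts can largely remove this dependence if events are dated.

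**What to change.** Before abstraction starts, amend Sections 12.3.1 and 14.3.1 and carry the same rules into the SAP:

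- Classify each device failure or re-intervention by its charted date, whichever review found it: on or before day 182 for the primary endpoint, on or before day 365 for the secondary.
- Date signs of failure by their first documentation. State in advance how signs first seen at a 6-month-window visit after day 182 are assigned, since their onset may lie on either side.
- Do not score a hip as a success by default when its charted follow-up ends before day 182. Either censor it at last contact and give Kaplan-Meier estimates at days 182 and 365, or report it as not evaluable, with a sensitivity analysis.
- Keep the ±91-day window for VAS and range of motion. Report the visit-window success rate with its Clopper-Pearson interval as a sensitivity analysis.
- Reconcile the qualifying visit in Section 11.2 (3 to 15 months) with the synopsis (6 to 15 months), because this decides whether hips seen only in the early half of the window can enter at all.

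The cost is wording plus the event and last-contact dates from charts already under review; no visits or subjects are added. The downside is that some event dates will be imprecise and need a stated imputation rule, and some hips with early last visits will be censored or not evaluable.

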7. LIST OF ABBREVIATIONS

Abbreviation	Term
ABHI	Association of British Healthcare Industries
ABS	Acrylonitrile Butadiene Styrene
ADE	Adverse Device Effect(s)
AE	Adverse Event(s)
ASADE	Anticipated Serious Adverse Device Effect
CFR	Code of Federal Regulations
CI	Confidence Interval
CRF	Case Report Form(s)
CSR	Clinical Study Report
CTA	Clinical Trial Agreement
CV	Curriculum Vitae
DevD	Device Deficiency(ies)
GCP	Good Clinical Practice
HHS	Health and Human Services
ICH	International Conference on Harmonisation
ICMJE	International Committee of Medical Journal Editors
IEC	International Ethics Committee
IFU	Instructions for Use
IP	Investigational Product
IRB	Institutional Review Board
ISF	Investigator Site File
ISO	International Organization for Standardization
LSV	Last subject, last visit

CONFIDENTIAL AND PROPRIETARY

This document contains information that is confidential and proprietary to Smith & Nephew PLC and Smith & Nephew, Inc. and is intended for use only by Smith & Nephew and its manufacturer. It shall not be reproduced or copied in whole or in part, nor shall the contents be disclosed by any means without prior written permission from Smith & Nephew, nor shall anyone make any use of it that is contrary to the expressed or implied wishes of Smith & Nephew.

Study Protocol—Device	
PMCF Study on PEEK Suture Anchors for Hip Indications	Number: 2018.14.SMD.PEEK.RET.HIP
	Version: 2.0, 03 April 2019
	Page: 28 of 63

Abbreviation	Term
MDR	Medical Device Regulation
N (or n)	Total Sample Size (or subgroup sample size)
NA or N/A	Not Applicable
PEEK / PK	Polyetheretherketone
PI	Principal Investigator
PMCF	Post-market Clinical Follow-up
PP	Per-protocol Population
ROM	Range of Motion
S&N	Smith & Nephew Inc.
SADE	Serious Adverse Device Effect(s)
SAE	Serious Adverse Event(s)
SAF	Safety Population
SAP	Statistical Analysis Plan
USADE	Unanticipated Serious Adverse Device Effect(s)
VAS	Visual Analogue Scale

CONFIDENTIAL AND PROPRIETARY

This document contains information that is confidential and proprietary to Smith & Nephew PLC and Smith & Nephew, Inc. and is intended for use only by Smith & Nephew and its manufacturer. It shall not be reproduced or copied in whole or in part, nor shall the contents be disclosed by any means without prior written permission from Smith & Nephew, nor shall anyone make any use of it that is contrary to the expressed or implied wishes of Smith & Nephew.

Study Protocol—Device	
PMCF Study on PEEK Suture Anchors for Hip Indications	Number: 2018.14.SMD.PEEK.RET.HIP
	Version: 2.0, 03 April 2019
	Page: 29 of 63

8. INTRODUCTION

Suture anchors are small fixation devices used in surgical procedures for attaching or reattaching tendons and ligaments to bone. The size and type of anchor used depends on the patient's bone density and the procedure performed.

Suture anchors are made of three components: the anchor which is inserted into the bone; the eyelet – which is a hole or a loop in the anchor that the suture passes through to link the anchor to the suture; and the suture – which is attached to the anchor through the eyelet of the anchor. An anchor- receiving hole is first drilled in the bone at the desired point of tissue reattachment. A suture anchor is deployed in the hole using an appropriate installation tool. This effectively locks the suture to the bone, with the free end(s) of the suture extending out the bone. Soft tissue is then moved into position over the hole containing the deployed suture anchor. As this is done, the free end(s) of the suture is (are) passed through or around the soft tissue so that the free end(s) of the suture reside(s) on the far (i.e., non-bone) side of the soft tissue. The suture is now used to tie the soft tissue securely to the bone.

Smith & Nephew offers a variety of suture anchors including several polyetheretherketone (PEEK) suture anchors soft tissue to bone repair. The PEEK devices included in study are all single use, sterile devices comprised of machined component anchor bodies that are manufactured from PEEK-OPTIMA Polymer (LT1). This material meets ISO 10993 biocompatibility requirements for implant devices, bone/tissue contact and permanent contact. The anchor tips are molded components which are also manufactured from PEEK-OPTIMA Polymer (LT3). PEEK-OPTIMA polymers provide an ideal combination of strength, biocompatibility, reviseability and inherent radiolucent characteristics. Smith & Nephew also provides a variety of reusable and disposable

CONFIDENTIAL AND PROPRIETARY

This document contains information that is confidential and proprietary to Smith & Nephew PLC and Smith & Nephew, Inc. and is intended for use only by Smith & Nephew and its manufacturer. It shall not be reproduced or copied in whole or in part, nor shall the contents be disclosed by any means without prior written permission from Smith & Nephew, nor shall anyone make any use of it that is contrary to the expressed or implied wishes of Smith & Nephew.

Study Protocol—Device	
PMCF Study on PEEK Suture Anchors for Hip Indications	Number: 2018.14.SMD.PEEK.RET.HIP
	Version: 2.0, 03 April 2019
	Page: 30 of 63

instrumentation used in conjunction with the suture anchors including awls, dilators, drills, guides, obturators and wires.

8.1 STUDY PURPOSE

The purpose of this study is to conduct post-market clinical follow-up regarding the safety and performance of the PEEK anchors as required per MDR.

8.2 SAFETY CONSIDERATIONS

Refer to the IFUs.

Table 2: Instructions for Use Reference Numbers

Instructions for use document numbers have been provided as a reference but may not have been the version used at the time of surgery.

PEEK Suture Anchor	IFU
Bioraptor Knotless Suture Anchor	10600479 2/17, Rev E
SpeedLock Hip Suture Anchor	P/N 62513 March 2017, Rev B

9. OBJECTIVE

9.1 PRIMARY OBJECTIVE

The primary objective of this study is to assess safety and performance post-market of the PEEK anchor devices in the hip.

CONFIDENTIAL AND PROPRIETARY

This document contains information that is confidential and proprietary to Smith & Nephew PLC and Smith & Nephew, Inc. and is intended for use only by Smith & Nephew and its manufacturer. It shall not be reproduced or copied in whole or in part, nor shall the contents be disclosed by any means without prior written permission from Smith & Nephew, nor shall anyone make any use of it that is contrary to the expressed or implied wishes of Smith & Nephew.

Study Protocol—Device	
PMCF Study on PEEK Suture Anchors for Hip Indications	Number: 2018.14.SMD.PEEK.RET.HIP
	Version: 2.0, 03 April 2019
	Page: 31 of 63

10. STUDY PRODUCT(S)

10.1 BIORAPTOR® KNOTLESS SUTURE ANCHOR

The BIORAPTOR® Knotless Suture Anchor is a single use, sterile, tap-in anchor that is manufactured from PEEK-OPTIMA® from Invibio®. The anchor is pre-assembled on an inserter comprised of a stainless steel shaft and an ABS and polycarbonate handle. The anchor is sized appropriately to facilitate both hip and shoulder procedures. The design consists of an outer anchor body and an inner shaft plug. The ribbed anchor, loaded with suture tails, is tapped into a pre-drilled prepared hole. The surgeon is now able to reapproximate the tissue to the appropriate tension and then use the torque-limiting knob on the insertion device that moves the inner plug down to lock the plug and achieve a secure fixation.

CONFIDENTIAL AND PROPRIETARY

This document contains information that is confidential and proprietary to Smith & Nephew PLC and Smith & Nephew, Inc. and is intended for use only by Smith & Nephew and its manufacturer. It shall not be reproduced or copied in whole or in part, nor shall the contents be disclosed by any means without prior written permission from Smith & Nephew, nor shall anyone make any use of it that is contrary to the expressed or implied wishes of Smith & Nephew.

Study Protocol—Device	
PMCF Study on PEEK Suture Anchors for Hip Indications	Number: 2018.14.SMD.PEEK.RET.HIP
	Version: 2.0, 03 April 2019
	Page: 32 of 63

